11.3. Retention samples

Retention samples will be taken at Screening and at Week 18/Early Termination. Not all samples might be analyzed, but all available viral test results will be listed, and a dedicated table will be prepared in case any seroconversion occurs at any time after administration of Panzyga.

11.4. Vital Signs

To evaluate short-term tolerance, monitoring of vital signs including blood pressure, body temperature, pulse and respiratory rate will be performed before, during and after end of each infusion at time points specified in the protocol. Vital sign abnormalities that qualify as AEs will be reported as such in the eCRF.

All available vital sign measurements will be listed and summarized by time-point by means of standard descriptive statistics, by actual treatment administered at the infusion in question as well as in total.

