The total dose for a single infusion cycle will be 2 g/kg BW (1 g/kg BW daily for two consecutive days). Patients will receive three infusion cycles at three-week intervals in the first phase of the study, followed by three additional infusion cycles at three-week intervals in the second blinded crossover phase of the study (patients previously in the Panzyga arm will be assigned placebo and patients previously in the placebo arm will be assigned Panzyga, administered at the same regimen).

If a patient is assigned placebo, the same volume and infusion rate as would have been applied in case of 2 g/kg BW Panzyga administration should be used. Therefore, placebo (0.9% w/v sodium chloride) will be administered at a dose of 20 mL/kg BW given over two consecutive days.

If AEs occur during the infusion, the infusion rate will be reduced to half the rate at which the event occurred, or the infusion will be interrupted until symptoms subside. The infusion may then be resumed at a rate tolerated by the patient. The administration of Panzyga 10% or sodium chloride 0.9% w/v must be completed within 8 hours after preparation. In case additional IMP is needed (e.g. lost or damaged), a separate IMP assignment via IRT transaction needs to be accomplished.

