4.2. Selection of Study Population

Patients will be aged 6–17 years, with moderate to severe PANS with prominent and stable obsessive-compulsive disorder (OCD) symptoms. All patients will meet criteria for PANS, including the abrupt dramatic onset of OCD meeting DSM-5 diagnostic criteria for OCD as confirmed by the Mini International Neuropsychiatric Interview for Children and Adolescents (MINI-KID), and at least two of seven additional associated neuropsychiatric symptoms. Please refer to the protocol for a complete list of inclusion/exclusion criteria.

As a possible consequence of the adaptations mentioned in section 4.1 the selection criteria for the study population may be adapted based on the recommendations of the IDMC. In such a case the study protocol will be amended to reflect the different selection criteria.

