Count data (the frequency of an event in a set time period): rate (count per unit time)

Continuous data (measurements on a continuous scale, including quasi-continuous variables): arithmetic mean, standard deviation, median, minimum, maximum

Scales data (Ordinal and Non-ordinal): absolute and relative frequencies

Time-to-event data (how long it takes to observe the outcome of interest: time to event or last evaluation (censored data in case patients are lost to follow-up) and event rate). These parameters might not be tabulated separately, but can be included as an inset into a Kaplan-Meier plot of the product-limit survival function estimates.

Additional descriptive and exploratory statistics, such as geometric means, quartiles or confidence intervals, are included as appropriate. If not mentioned otherwise, confidence intervals are to be understood as two-sided, 95% confidence intervals.

Categorical data will generally be summarized with counts and percentages of patients. The denominator used for the percentage calculation will be clearly defined.

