11.2. Clinical Laboratory Evaluations

All laboratory data will be converted to standard units during the Data Management process. The laboratory data will be listed with suitable flags indicating abnormal values (L=Lower than reference range, H=Higher than reference range).

Summary statistics for the laboratory values as well as their changes from baseline will be tabulated for all laboratory parameters. The tables on changes in lab parameters will again feature columns for each treatment group as defined above and a total column in a side-by-side fashion.

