12.2. Population Summary Conventions

- Population(s) represented on the tables or data listings will be clearly identified in the title as “Population: <name of population>” where <name of population> is any of the analysis population names or abbreviations defined in section 7 (full analysis set (FAS), per-protocol set (PP), etc.).

- Sub-population(s) or special population(s) descriptions will provide sufficient detail to ensure comprehension of the population (e.g., FAS Females, Per-Protocol Patients with prophylactic use of antibiotics) used for analysis in a table or figure.
- Population sizes may be presented for each treatment or dosing category as totals in the column header as (N=xxx), where appropriate.
- Population sizes shown with summary statistics are the samples sizes (n) of patients with non-missing values.
- All population summaries for continuous variables will include: N, mean, SD, median, Q1, Q3, minimum and maximum.
- All percentages are rounded and reported to a single decimal point (xx.x%).

Property of Octapharma. Do not copy or distribute without written permission.

13. Tables, Listings and Figures

To be supplied in a separate document later when all feedback from authorities will be available.

Property of Octapharma. Do not copy or distribute without written permission.

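### SAP 11.4 names raw vital signs by time-point but no change from the pre-infusion value, so a rise or fall within an infusion in a few children may not show in the tables

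*SAP*

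**What the plan says.** SAP 11.4 gives its purpose as short-term tolerance. Blood pressure, temperature, pulse and respiratory rate are monitored, and this "will be performed before, during and after end of each infusion at time points specified in the protocol". A pre-infusion value is therefore planned at every infusion.

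For the analysis, every reading is to be listed, and the readings are to be "summarized by time-point by means of standard descriptive statistics, by actual treatment administered at the infusion in question as well as in total". The statistics are those of SAP section 8 for continuous data ("arithmetic mean, standard deviation, median, minimum, maximum"), extended in SAP 12.2: "All population summaries for continuous variables will include: N, mean, SD, median, Q1, Q3, minimum and maximum". The visible text of 11.4 names no change from the pre-infusion value, no worst value per infusion and no limit for counting abnormal readings.

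SAP 11.2 treats laboratory data differently: "Summary statistics for the laboratory values as well as their changes from baseline will be tabulated for all laboratory parameters". It also flags values outside the reference range in the listings.

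The tables pool the whole age range ("Patients will be aged 6–17 years", SAP 4.2), and 11.4 names no age grouping.

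**The concern.** Tolerance of an infusion is a within-child, within-infusion question: what happened to this child's pressure, pulse, temperature or respiration after the infusion began. A column of raw values at one time-point answers a different question, namely where the whole group stands at that moment. In a group aged 6 to 17, much of the spread in raw readings comes from stable differences between children, partly through age. A large fall in an older child can end at a value that is ordinary for a younger one, and so leave the mean, the SD and even the minimum little altered.

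At stake is how well a descriptive safety table serves its own stated aim. Protocol 1.3 lists low blood pressure and fever among the reactions that may occur, and says that patients new to IVIG are at more risk. Exclusion criterion 12 bars earlier IVIG for neuropsychiatric symptoms, so many of these children will be new to it.

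**Working it through.** The documents give no figure on this point, so there is none to reproduce. Every number in steps 1 to 4 is an assumption for illustration, using systolic pressure.

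**Inputs (assumed).** Ages uniform over the whole years 6 to 17; pressure rising 1 to 2 mmHg per year of age; between-child SD 8 mmHg at a given age; within-infusion SD 6 mmHg; 5% to 10% of infusions with a true fall of 25 or 30 mmHg.

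**1. Spread of raw values.** Twelve equally likely ages have variance (12² − 1)/12 = 11.92.
- Slope 1: SD = √(1 × 11.92 + 64 + 36) = 10.6 mmHg.
- Slope 2: SD = √(4 × 11.92 + 64 + 36) = 12.2 mmHg.

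**2. Spread of the change.**
- If the pre-infusion reading carries no noise of its own, SD = 6.0 mmHg.
- If it carries the same noise as the later reading, SD = 6 × √2 = 8.5 mmHg.

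**3. Share of true falls that stay hidden.** Call a fall hidden if it lies above the lower 2.5% limit of the infusions without a reaction. For a fall D this share is P(Z > (D − 1.96 × SD)/SD).

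| Measure | SD (mmHg) | D = 25 | D = 30 |
|---|---|---|---|
| Raw, slope 1 | 10.6 | 34% | 19% |
| Raw, slope 2 | 12.2 | 46% | 31% |
| Change, no noise in the pre-infusion value | 6.0 | 1% | 0% |
| Change, equal noise in the pre-infusion value | 8.5 | 16% | 6% |

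A simulation of 400,000 infusions agrees with each cell to within about one percentage point.

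**4. Group mean.**
- Complete data: the mean shift is p × D, so 0.05 × 25 = 1.25 mmHg up to 0.10 × 30 = 3.0 mmHg. It is the same for raw values and for the change, because the mean of the differences equals the difference of the means.
- Half of the reacting infusions without the later reading: (p/2 × D)/(1 − p/2), which is 0.64 mmHg for p = 0.05 and D = 25, and 1.58 mmHg for p = 0.10 and D = 30, again for either measure.
- All of them without it: the shift is 0 for either measure.

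So the change helps to identify individual reactions. It does not enlarge a mean shift, and it does not recover lost readings.

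**5. When the gain disappears.** With equal variances before and during, SD(change)/SD(raw) = √(2(1 − r)), where r is the within-child correlation. This is 1.00 at r = 0.5, 0.77 at r = 0.7 and 0.45 at r = 0.9. At r = 0.5 or below, the change is no less variable than the raw value.

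**The case against.** The strongest reply is that this table is not how the trial judges tolerance. SAP 11.4 also sends qualifying vital-sign abnormalities to the adverse event pages. SAP 11.1 tabulates infusional events during an infusion or within 1, 24 and 72 hours of it. Protocol 7.5 counts other adverse events within short-term tolerance and relates events to infusion rate, and every reading is listed. This stands: a reader who infers that tolerance rests on raw vital signs alone goes beyond the documents. It does not close the gap. Protocol 7.3.8 leaves it to judgement whether an isolated abnormal reading becomes an event, with no numeric limit in the visible text, and a listing does not summarize.

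A reader might also infer that age differences mask a Panzyga effect. The documents do not support that. Treatment is randomized 1:1, and under Protocol 3.3.2 each child is planned to receive both products, so the age mix should be similar in the two columns. Age adds spread and should not bias the contrast.

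A third tempting inference is that interrupted infusions lose their later readings and so flatter the later means. Protocol 5.4 does say that after an adverse event "the infusion rate will be reduced to half the rate at which the event occurred, or the infusion will be interrupted until symptoms subside". But the vital-sign schedule (Protocol 7.3.8) and the visit procedures (6.1) are redacted or unreadable. Readings are planned after the end of each infusion, interrupted infusions may resume, and children are observed for at least an hour afterwards. Loss of readings is possible and cannot be shown. The n required by SAP 12.2 would reveal missing values, though not their cause.

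Finally, Protocol 9.2.3 is unreadable and the list of tables is deferred to a separate document. Either may specify more, so the point is confined to the visible text of SAP 11.4.

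**Conclusion.** The point holds in a limited form. As published, SAP 11.4 summarizes raw vital signs by time-point and actual treatment, and names neither a within-infusion change nor a preset limit. Pooled over ages 6 to 17, such summaries are a weak way to detect an individual rise or fall.

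On the assumed values, 19% to 46% of falls of 25 to 30 mmHg would stay within the ordinary raw range; the rest, 54% to 81%, would lie below it, so raw extremes can still show some reactions. With the change, the hidden share is 0% to 16%, depending on the noise in the pre-infusion reading. This advantage needs a within-child correlation clearly above 0.5, and group means are unaffected.

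Vital signs are exploratory and descriptive here, and no hypothesis test depends on this table. It is a minor safety-reporting improvement with no bearing on the primary analysis.

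**What to change.** Keep the raw summaries and add to SAP 11.4, by actual treatment:

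- (a) the change from the same day's pre-infusion value at each time-point;
- (b) the largest rise and the largest fall per infusion, with every started infusion in the denominator and the number without any reading after the start shown;
- (c) the number and percent of infusions beyond age-appropriate limits, fixed before unblinding and used for analysis only, not to guide care.

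Item (b) keeps slowed or stopped infusions visible through whatever readings were taken; the change in (a) alone would not do so. A child can contribute up to 3 cycles × 2 days = 6 infusions of each product, so the infusion counts are not independent and should be read as descriptive.

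The cost is a few lines of SAP text, the programming, and one more set of descriptive tables. No new measurement is needed. If the separate table list or Protocol 9.2.3 already contains these summaries, a cross-reference in 11.4 is enough.

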11.5. Physical Examination

General and targeted physical examinations respectively will be performed throughout the study at visits specified in the protocol. All documented abnormalities will be listed, and any clinically relevant worsening from the status at baseline will be documented as an AE.

12. Reporting Conventions

The following reporting conventions will be adopted for the presentation of study data. These conventions will enhance the review process and help to standardize presentation with common notations.

12.1. General Reporting Conventions

- All tables and data listings will be developed in landscape orientation, unless presented as part of the text in a CSR.
- Figures will in general also be presented in landscape orientation, unless presented as part of the text in a CSR.
- Legends will be used for all figures with more than one variable or item displayed.
- Figures will be in black and white, unless color figures have been identified as useful for discriminating presentation in the figure. Lines in figures should be wide enough to view the line after being photocopied.
- Specialized text styles, such as bolding, italics, borders, shading, superscripted and subscripted text will not be used in tables, figures, and data listings unless they add significant value to the table, figure, or data listing.
- Only standard keyboard characters should be used in tables and data listings. Special characters, such as non-printable control characters, printer specific, or font specific characters, will not be used on a table, figure, or data listing. Hexadecimal character representations are allowed (e.g., μ , α , β).
- The ICH numbering convention is to be used for all tables, figures, and data listings.
- All footnotes will be left justified and placed at the bottom of a page. Footnotes must be present on the page where they are first referenced. Footnotes should be used sparingly and must add value to the table, figure, or data listing. If more than four footnote lines are planned then a cover page may be used to display footnotes.
- Missing values for both numeric and character variables will be presented as blanks in a table or data listing. A zero (0) may be used if appropriate to identify when the frequency of a variable is not observed.
- All date values will be presented as DDMMYYYY (e.g., 29AUG2001) format.
- All observed time values will be presented using a 24-hour clock HH:MM format (e.g. 15:26).
- Time durations will be reported in HH:MM notation. The use of decimal notation to present (display) time durations should be avoided (e.g. 0.083h = 5min) unless it is necessary to show the computation of time differences in a table, figure, or data listing, in which case both notations may be used to display the time duration.
- All tables, figures and data listings will have the name of the program, and a date stamp on the bottom of each output.

12.2. Population Summary Conventions

- Population(s) represented on the tables or data listings will be clearly identified in the title as “Population: <name of population>” where <name of population> is any of the analysis population names or abbreviations defined in section 7 (full analysis set (FAS), per-protocol set (PP), etc.).

- Sub-population(s) or special population(s) descriptions will provide sufficient detail to ensure comprehension of the population (e.g., FAS Females, Per-Protocol Patients with prophylactic use of antibiotics) used for analysis in a table or figure.
- Population sizes may be presented for each treatment or dosing category as totals in the column header as (N=xxx), where appropriate.
- Population sizes shown with summary statistics are the samples sizes (n) of patients with non-missing values.
- All population summaries for continuous variables will include: N, mean, SD, median, Q1, Q3, minimum and maximum.
- All percentages are rounded and reported to a single decimal point (xx.x%).

Property of Octapharma. Do not copy or distribute without written permission.

13. Tables, Listings and Figures

To be supplied in a separate document later when all feedback from authorities will be available.

Property of Octapharma. Do not copy or distribute without written permission.
